Asthma is the most common chronic condition among children, a leading reason for pediatric hospitalization in the United States, and a leading cause of potentially preventable pediatric admissions.¹ Hospital readmissions and emergency room utilization is common among children with asthma, and is responsible for a large economic burden on the healthcare system with \$1.5 billion in hospital charges annually in the US² and approximately \$6 billion in estimated direct healthcare costs.³

Many strategies for decreasing asthma-related emergency department (ED) visits and hospital admissions have been investigated.⁴ The most successful interventions have involved increasing asthma education and teaching of self-management techniques to patients and their families.⁵ Traditional teaching is often limited by fragmented or rushed sessions on the day of discharge from the hospital or ED, or during time-limited follow up visits at the clinic. Other strategies such as comprehensive home visits, specialized asthma clinics, or community-based initiatives, although effective, are costly and resource intensive.⁶⁻⁸

Given the limited time for patient-provider interaction, there's a need to develop more efficient ways for healthcare providers to interact with patients and parents outside medical settings. Social media is a forum that could provide more frequent contact with patients and families, and allow for continuing education. It is estimated that more than 70% of the U.S population uses some form of social media.⁹ For teenagers, this usage jumps to over 90%. About 95% of teenagers have access to a smart phone and 45% of teenagers report being online on a near constant basis.¹⁰ Reaching this age group may be of particular importance, as it has been shown that adolescents have decreased compliance, increased improper usage with asthma treatments, and comprise of a large proportion of hospital readmissions and emergency room utilization.¹¹⁻¹³

Social media is a promising tool to provide education. Previous studies have used social media in a wide range of topics to provide education to both patients and clinicians. Positive effects have been seen in adults in promotion of breastfeeding, diabetes management, dementia management, and reproductive health education in adolescents¹⁴⁻¹⁷. Studies have also supported the use of social media as improving learning, engagement, and motivation in learners.¹⁸

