Snapchat is a mobile app for Android and iOS devices that is primarily a photo based social media platform. It has over 80 million users in the United States. In terms of age distribution, 69% of teenagers, and 24% of adults use the platform. Among teenagers, it is the social media platform that they use most often.^{9,10} While most “snaps” are made available to the receiver for only a short time before it becomes inaccessible, Snapchat has a “snapcode” feature that functions similarly to QR reader. This can be used to open an internet link through the Snapchat application. A previous study has used this feature to promote reproductive health education in hospitalized adolescents.¹⁷

Social media is now a part of daily life for the majority of Americans and particularly for adolescents. Given that social media is already a forum utilized by our patients and families, using it seems like a promising resource inexpensive modality to provide consistent asthma education.

Specific Aims:

[figure not shown]
1. To randomize 200 eligible children with asthma to social media enhanced education or to usual care to evaluate whether SME will:
 - a. Reduce total number of treatment days defined as summation of days of subsequent hospital admission, emergency room visits, and clinic visits
 - b. Reduce missed school days
 - c. Reduce total costs from a health system perspective
 - d. Have increased effect with increased social media engagement
 - e. Have increased effect in participants with both caregiver and patient (combined) with social media accounts, compared to participants where only the patient or only the caregiver uses social media (single)
 - f. Have increased patient satisfaction in the asthma education received
2. To obtain the experience and data needed to refine SME to be able to expand this platform for other chronic medical conditions with high healthcare utilization including pediatric diabetes, epilepsy, and sickle cell disease

Hypotheses: Social media enhanced education will result in

1. Reduction in treatment days in a medical setting from enrollment to one year from enrollment (primary hypothesis)
2. Reduction in missed school days
3. Reduction in total health system costs
4. Increased treatment effect in those patients with high social media engagement compared to low social media engagement
5. Increased treatment effect in those with combined (patient + caregiver) social media accounts compared to single participants

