Usual Asthma Education: (which will not be modified by the study protocol) For patients who are admitted to Children's Memorial Hermann for asthma exacerbation, asthma education is provided to patients and families on the day of discharge by the nurse and respiratory therapist. Respiratory therapists spend approximately 20-30 minutes educating on the following topics: Triggers, Signs & Symptoms, Medication Use, Medication Delivery, Peak Flow, Zones and how to respond to each, and Cleaning equipment. Nursing staff are responsible for printing out education sheets to give to patients and showing an education video that is ~20 minutes long. An asthma action plan (paperwork with a plan of action ie. how many puffs of albuterol to take, when to come to the emergency room, etc.) are given to families on discharge. Patients that are discharged from the emergency room are given the same educational materials by the nurses and/or respiratory therapists except for the asthma video. Patients receive a variable amount of asthma education when going to usual clinic visits. The education provided is dependent on the provider, and usually limited in length to the time of the visit (~10-20 minutes).

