3. Participants will have an informal avenue of communication to the team by tweeting questions or comments to the team.

Instagram

The research team will post photos and short videos to be shared with participants. Participants can comment on the posts to discuss or ask questions to the team.

Snapchat

The research team will post pictures and videos similar to the Instagram platform. The team will also create snapcodes that link participants to our cloud based asthma education website run via google drive. This will allow for text based education along with the typical photo based content of this platform.

Outcomes:

Primary Outcome: Total number of treatment days in a medical setting (hospital, ED, clinic) within one year of enrollment. Treatment days are defined as the summation of days in the hospital, ED, or in the clinic. We chose one year because of the chronicity of asthma, as well as its seasonal variation.

Secondary Outcomes: Total number of hospitalizations, total number of readmissions, total number of emergency room visits, and the total number of clinic visits, patient satisfaction and understanding of asthma education, number of missed days of school, and total estimated health system costs, hospital costs, and clinic costs.

Healthcare utilization will be primarily assessed by parental report. The PI will contact families every month and ask if their child had been admitted, visited the emergency room, had a clinic appointment for asthma, or missed any days of school within that month. We will also verify utilization of any of the 14 Memorial Hermann hospitals (MHHS) and the UT Health clinics from their respective electronic medical records and claims data. While we are aware of the risk of recall bias, we believe a contact every month is frequent enough to minimize the bias. We will also obtain multiple ways of contact (phone call, text, email, social media) in order to reduce loss to follow up.

Level of engagement will be tabulated by the following: Facebook engagement will be tracked through “likes,” comments, unfriending, completion of learning units, completion of polls. Twitter engagement will be tracked through “retweets,” comments, completion of polls, and unfollowings. Instagram engagement will be tracked by “likes,” comments, and unfollowings. Snapchat engagement will be tracked by number of snapcode links viewed, and any unfollowings.

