Hospital and clinic costs will be assessed from the health system perspective. For each ED visit and hospitalization in the MHHS, total hospital-specific costs will be obtained from the cost-accounting system for these hospitals. Costs for physician services provided at CMHH will be estimated using UTHealth claims data and Relative Value Units (RVUs) from the Medicare Fee Schedule. The costs at other hospitals outside MHHS will be estimated based on the mean costs of these encounters at MHHS. Costs for clinic visits at UT Health will be estimated using UTHealth claims data and using the standard RVU-based method. The costs for office visits occurring outside our center will be estimated based on the mean costs observed at UTHealth. For the social media intervention group, we will also add the costs of the personnel time spent curating and managing the educational material to be used in the social media platforms. The total time spent with the social media intervention will be prospectively collected by the PI (who will be primarily responsible for managing the social media intervention and will also include time from the pulmonologist [RM] and hospitalist [KS] whenever their input is required) and will then be multiplied by the unit time costs based on the personnel salary, fringes, and overhead costs. All costs will be inflated to the year of analysis based on the Consumer Price Index for medical services.

Data Analysis Plan:

Effect size, recruitment, power & statistical analysis

Based on retrospective data of patients hospitalized at CMHH as well as estimated national data,^{27,28} we estimate a 25% hospital readmission rate and 35% emergency visit rate within one year of discharge for those receiving usual asthma education. We also assume a 35% unplanned clinic visit rate within one year of discharge. Each admission accounts for 2.4 treatment days, and each clinic and ER visit accounts for 1 treatment day. In a population of 100 patients, we then expect the total number of treatment days to be 114 days or 1.14 days per child-year. With an expected 25% effect size (based on the 20%-30% effect size reported in the Cochrane reviews on the impact of asthma education on healthcare utilization among pediatric patients,⁴ recruitment of 200 patients will give 0.80 power to show reduction in total number of unplanned treatment days with probability of benefit >60%.

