Information to be gathered will be missed school days, total number of hospitalizations, emergency room visits, and clinic visits. We will also gather costs of these visits. Engagement data will be obtained from the various social media platforms.

Interpretation and Potential Importance of Findings:

If we are able to demonstrate successful effects of social media enhanced asthma education in decreasing unplanned healthcare utilization, we believe the impact to be substantial. First, there is a large disease burden. Asthma is the most common chronic disease in childhood that affects 5.5 million children in the United States. Second, the intervention is easily implementable since social media use is so ubiquitous. Third, the outcome of a cost dominant intervention has implications for tremendous savings on costs to the healthcare system. Compounding this, we think the results of the study would be easily generalizable – 1. To the adult population, encompassing another 19.2 million patients with asthma in the US (339 million worldwide), and 2. To other chronic pediatric medical conditions that have frequent unplanned healthcare utilization such as pediatric diabetes, sickle cell, and epilepsy.

Plans for Dissemination of Results:

Once the project is completed, we plan on dissemination of results through submissions to national conferences (Pediatric Academic Societies, American Academy Pediatrics, and Pediatric Hospital Medicine) as well as manuscript publication in a peer-reviewed journal (JAMA Pediatrics, Pediatrics, Hospital Pediatrics).

References

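### The primary outcome counts every clinic day, but the power statement and the interpretation concern unplanned care, so the 0.80 power is not shown to apply to the outcome as written

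*Combined protocol and SAP*

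**What the plan says.** **Outcome side.** The Outcomes section sets the primary outcome as "Total number of treatment days in a medical setting (hospital, ED, clinic) within one year of enrollment" and defines treatment days as the sum over the three settings. Specific Aim 1a and the primary hypothesis use the same count. None of them is limited to unplanned visits. At the monthly contact the principal investigator will "ask if their child had been admitted, visited the emergency room, had a clinic appointment for asthma". The restriction to asthma comes from that question; the outcome definition does not contain it. The list of information to be gathered under Study Procedures names clinic visits without dividing them by type.

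**Power and interpretation side.** The Data Analysis Plan states: "We also assume a 35% unplanned clinic visit rate within one year of discharge". It adds a 25% readmission rate at 2.4 days each and a 35% emergency visit rate, assumes a 25% effect, and concludes that 200 patients give "0.80 power to show reduction in total number of unplanned treatment days" with probability of benefit above 60%. The interpretation section describes success as "social media enhanced asthma education in decreasing unplanned healthcare utilization". The second title also says *unplanned*; the first does not.

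**Routine clinic contact.** The description of usual care says: "Patients receive a variable amount of asthma education when going to usual clinic visits". The Background mentions teaching "or during time-limited follow up visits at the clinic", though only as a general remark about how asthma education is delivered.

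No section excludes planned visits from the outcome, and none gives them a rate, a variance or an expected effect.

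**The concern.** Children just discharged after an asthma admission can be expected to have some routine follow-up. Under the outcome as written each such visit adds a treatment day; under the power calculation it adds nothing. What that does to the result depends on how social media education (SME) affects routine visits:

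- If it leaves them unchanged, they pull the rate ratio toward 1.
- If it prompts more of them, they offset a real reduction in acute care.
- If it reduces them, fewer routine visits are scored as benefit and, in the language of the interpretation section, could be reported as less unplanned care.

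At stake are whether the stated power describes the primary analysis, and whether the primary result can carry a conclusion about unplanned utilization.

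**Working it through.** **Inputs from the Data Analysis Plan.** 100 children per arm; rate ratio 0.75 on unplanned days; SD 1.5 times the mean; success if the posterior probability of a rate ratio below 1 exceeds 0.60; prior interval 0.3 to 3.0. I take the prior as normal on the log rate ratio with mean 0 and SD ln(3.0/0.3)/(2 × 1.96) = 0.587. Using ln(3)/1.96 = 0.561 instead moves no power figure by more than about 0.001. The control mean mu is 1.14 as stated. The plan's own rates give 25 × 2.4 + 35 + 35 = 130 days per 100 children, or 1.30, so both are carried. That discrepancy is a separate matter and barely affects power.

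**Formulas.** With P planned visits per child-year in the control arm and g the ratio by which SME changes them:

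- Mc = mu + P; Mt = 0.75 mu + gP; RR = Mt/Mc
- SE² = Vc/(100 Mc²) + Vt/(100 Mt²)
- w = 0.587²/(0.587² + SE²)
- power = Φ(−ln RR/SE − 0.253/√w)

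**The plan's own figure (P = 0).**

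- SD 1.5 times each arm's own mean: SE² = 2 × 2.25/100 = 0.045, SE = 0.212, w = 0.885. Power = Φ(0.288/0.212 − 0.269) = 0.86.
- Constant negative binomial dispersion: power = 0.85.
- Control-arm SD in both arms: SE² = 0.0225 + 0.0225/0.75² = 0.0625, SE = 0.25, w = 0.847. Power = Φ(1.151 − 0.275) = 0.81. This makes the SME-arm SD 1.5/0.75 = 2.0 times its own mean.

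So 0.80 is roughly met under the last reading and is about 5 to 6 points low under the others.

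**Adding planned visits.** The rate (P = 1 or 2) and the effect g are my assumptions. Planned visits are taken as independent and Poisson, so they add variance P in the control arm and gP in the SME arm.

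One cell in full, with mu = 1.14, P = 1, g = 1 and own-arm SD:

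- Mc = 2.14, Mt = 0.855 + 1 = 1.855, RR = 0.867
- Vc = 1.71² + 1 = 3.924; Vt = 1.2825² + 1 = 2.645
- SE² = 0.00857 + 0.00769 = 0.01625, SE = 0.1275, w = 0.955
- power = Φ(1.121 − 0.259) = 0.81

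Ranges over mu = 1.14 or 1.30, P = 1 or 2, and own-arm or control-arm SD for the unplanned part:

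| Planned visits under SME | RR | Power |
|---|---|---|
| Unchanged (g = 1.0) | 0.86–0.91 | 0.74–0.82 |
| Up 10% (g = 1.1) | 0.90–0.97 | 0.50–0.71 |
| Down 30% (g = 0.7) | 0.72–0.73 | 0.96 or more |

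In the unchanged row, P = 1 with own-arm SD gives 0.81 to 0.82, so that case shows no shortfall. The 30% in the last row is the plan's cited figure for clinic visits under asthma education; applying it to planned visits is an assumption.

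**Where the reduction comes from when g = 0.7.** The planned share is 0.3P/(0.3P + 0.25 mu): 0.51 and 0.68 for mu = 1.14 with P = 1 and 2, and 0.48 and 0.65 for mu = 1.30.

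**A pessimistic bound.** Applying SD = 1.5 × mean to the enlarged total gives 0.56 to 0.67 when planned visits are unchanged. At mu = 1.14 and P = 1, independent planned visits would then need an SD of √((1.5 × 2.14)² − (1.5 × 1.14)²) = 2.72 on a mean of 1. The plan uses total treatment days for the 1.14 built from unplanned visits, so its SD rule most naturally refers to that quantity.

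**The case against.** The strongest reply is that this is loose wording in a pilot. The plan disclaims a success threshold and says that conclusions will rest on the probability of benefit, meaning a reduction in treatment days and in cost, which agrees with the outcome definition. The word *unplanned* in the interpretation section sits in a conditional paragraph on impact, which is not an analysis rule. Hospitalizations and emergency visits are separate secondary outcomes, so a total driven by clinic visits would be noticed. The follow-up script is listed as an attachment but not shown, and may already classify visits.

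Much of this stands and limits the harm. It does not remove the mismatch. In the sample-size paragraph *unplanned* defines a numerical input and names the powered quantity. The secondary outcomes separate settings, but the total clinic-visit count still mixes planned with unplanned. Even if the script separates them, the outcome definition and the power statement disagree.

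A reader might infer that the trial is underpowered for its primary outcome. The documents do not support that. Every shortfall above needs an assumed planned-visit rate together with an assumed effect on planned visits, and a fall in planned visits can raise power well above 0.80.

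**Conclusion.** The inconsistency is plain in the text and worth correcting. The outcome as written is all hospital, emergency and clinic days; the 0.80 power and the intended conclusion concern unplanned care. The supportable claim is that 0.80 has not been shown to apply to the outcome as written, and that power there could be lower or higher.

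For unplanned days the plan's inputs give 0.81 to 0.86. For all days the answer runs from 0.50 to above 0.96 over the assumed Poisson scenarios, which mainly shows that the power is unspecified. These figures rest on an assumed 1 to 2 planned visits per child-year, independence of planned and unplanned days, and the normal approximation. The figures of 0.56 to 0.67 are a bound and should not be quoted as the expected power.

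It would also go too far to say that the trial cannot distinguish visit types, because the script is not available to check.

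**What to change.** Make the outcome, the power statement and the interpretation name the same quantity. Either of two routes would do.

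(a) Keep all treatment days as primary. Restate the power over a stated range of planned-visit rates and effects, and remove *unplanned* from the second title, the power statement and the interpretation section. This costs only text, together with a wider or less favourable power figure.

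(b) Define the primary outcome as unplanned asthma treatment days, which fits the second title, the sample-size paragraph and the interpretation section. Record at the monthly contact whether each clinic visit was booked in advance as routine follow-up, check this against Memorial Hermann and UT Health records where available, and report all-visit days as a secondary outcome. This costs revised outcome wording, at most one item in a contact that already takes place, and a record check. Its drawback is possible misclassification that differs by arm, because families are unblinded, as is the principal investigator who runs the intervention and makes the contacts, and the records cover only those two systems. The all-visit secondary outcome would serve as the sensitivity check.

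Neither route adds patients or study contacts.

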6. Increase in patient satisfaction of amount and frequency of asthma education.

Study Design and Methods:

Logic Model: Using Social Media to Enhance Asthma Education

Population: We will recruit children age 3-17 years old hospitalized to Children's Memorial Hermann admitted for asthma exacerbation. To be eligible, the patient and/or primary caregiver must have internet access on cellular phones or at home and use a social media account (Facebook, Twitter, Instagram, and/or Snapchat). Exclusion criteria include children with other chronic conditions besides asthma that may necessitate frequent health care utilization. i.e. children with complex chronic conditions, sickle cell, seizures, diabetes. Children less than 3 years are excluded as a formal diagnosis of asthma prior to this age is difficult, and we aim to homogenize the population and exclude similar diagnoses such as bronchiolitis or wheezing of infancy.

Randomization, Consent, Allocation, Blinding: The PI (RPC) will be primarily responsible for enrollment and randomization. We will submit our study to the UTHealth Institutional Review Board as a quality improvement (QI) trial to verify the benefits of an intervention to increase access to asthma education beyond what would otherwise be provided in usual care. As allowed under federal regulations for QI studies judged unlikely to increase patient risk,²³⁻²⁵ we will request waiver of consent from the IRB, but we plan to still seek verbal permission to be able to contact patients monthly to assess their healthcare utilization.

Block randomization with variable block sizes and stratification by age will occur. Stratification for age will occur, (3-11 years or 12-17 years) to allow for equal allocation of teenagers to each arm. Allocation ratio of 1:1 will be used. Patients will be randomized during their hospitalization. While patients and caregivers cannot be blinded, the statistician and healthcare economist will be.

Interventions:

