All statistical and economic analyses will be conducted under the intent-to-treat analyses principle using generalized linear models with appropriate link function based on data distribution (ie, negative binomial or Poisson with log link). All Bayesian models will use neutral, vaguely informative prior such as those with relative risk centered at 1 with credible interval range from 0.3-3.0 encompassing the largest likely effect size for major outcomes in RCTs. Cost differences between the two arms will be assessed using generalized linear models with log-link and gamma distribution. To account for patients who may not be hospitalized or incur hospital-related costs during the study period, zero-inflated models will be considered. All models will be adjusted for stratifying variables (asthma control, recruitment site, and age) and account for patient clustering as necessary. Optimal model fit for each outcome will be determined from model diagnostics and comparison of likelihood-based statistics. All analyses will be conducted in R.

Data Storage and Handling: We will use Research Electronic Data Capture (REDCap) to randomize patients and collect predefined study data needed to address each of our hypotheses. REDCap is a secure, web-based application designed to support data capture for research studies, providing: 1) an intuitive interface for validated data entry; 2) audit trails for tracking data manipulation and export procedures; 3) automated export procedures for seamless data downloads to common statistical packages; and 4) procedures for importing data from external sources

Study Procedures: Participants will be approached for enrolment during their index hospitalization. Consent will be obtained. Study duration will last one year from enrolment. Participants will be contacted once a month (12 contacts total) to assess healthcare utilization within that past month. The PI on enrollment will ask for several different methods of contact and ask which the participants prefer ie. calling - what times of day/day of week, emailing, texting, directly messaging on social media etc. The PI will contact each participant by their mode of preference once a month. During the follow up contacts, participants will also be asked a short questionnaire (approximately 10 minutes).

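### The primary outcome has two conflicting definitions: Aim 1a counts only subsequent admissions, while the Outcomes section does not exclude the rest of the index stay

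*Combined protocol and SAP*

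**What the plan says.** All references are to the combined protocol and SAP.

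- **Outcomes, Primary Outcome:** "Total number of treatment days in a medical setting (hospital, ED, clinic) within one year of enrollment". The next sentence reads "Treatment days are defined as the summation of days in the hospital, ED, or in the clinic". Neither sentence mentions the index admission. Hypothesis 1 also starts the year at enrollment.
- **Specific Aims, 1a:** "Reduce total number of treatment days defined as summation of days of subsequent hospital admission, emergency room visits, and clinic visits". Here hospital days are restricted to later admissions.
- **Randomization, Consent, Allocation, Blinding:** "Patients will be randomized during their hospitalization". Study Procedures agrees: "Participants will be approached for enrolment during their index hospitalization".
- **Data Analysis Plan, effect size and power:** "we estimate a 25% hospital readmission rate and 35% emergency visit rate within one year of discharge for those receiving usual asthma education". The unplanned clinic visit rate is also counted from discharge.
- **Outcomes, cost paragraph:** hospital costs are collected for each ED visit and hospitalization in the hospital system. The text does not say whether index-stay cost after enrollment is included.
- **Outcomes, Secondary Outcomes:** hospitalizations and readmissions are listed as separate counts, and neither is defined.

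**The concern.** An analyst who programs the primary outcome from the Outcomes section alone would start each child's count at an enrollment that takes place on the ward, and would include the inpatient days still to come. An analyst who works from Aim 1a would not. The two would report different ratios from the same data.

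The remaining index days depend on the presenting exacerbation and on how early in the stay the child was approached. It is a reasonable inference, though not stated in the documents, that education posted about weekly cannot change the rest of a stay planned at 2.4 days. Such days would add a similar amount to both arms. The planned models use a log link and so report ratios, and a shared constant moves a ratio toward 1. The trial aims to estimate the magnitude of benefit and to inform expansion, so the reported effect should not depend on which section the analyst followed.

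**Working it through.** **1. Inputs from the plan.** 25% readmission, 35% ED visits and 35% unplanned clinic visits, all within a year of discharge; 2.4 days per admission and 1 day per ED or clinic visit; stated control mean 1.14 days per child-year; 25% reduction; 200 children randomized 1:1; negative binomial with SD 1.5 times the mean; success if the posterior probability of benefit exceeds 60%; stated power 0.80. The prior on the relative risk has a credible interval of 0.3 to 3.0. It is taken as centred at 1, as in the analysis text; the power text says 0, which fits the log scale.

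**2. Input not in the plan.** r is the mean number of index days left after enrollment. Assumed range: 0 (enrolled as the stay ends) to 2.4 (the planning length of a whole admission, used as an upper scenario).

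**3. The plan's own figures.** Control mean = 0.25 × 2.4 + 0.35 + 0.35 = 1.30, not 1.14. This mismatch is a separate matter, so both means are carried below. No term represents the index stay, so neither mean contains index days.

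Power, by closed form, is Φ(d/se − z(0.60)/√w):
- d = −ln 0.75 = 0.288
- se = √(1.5²/100 + 1.5²/100) = 0.212
- prior SD = ln 3/1.96 = 0.561
- w = 0.561²/(0.561² + 0.212²) = 0.875
- power = Φ(1.356 − 0.253/0.935) = Φ(1.085) = 0.86

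Simulation with a fitted negative binomial model (2,000 runs) gives 0.85 to 0.86 at a mean of 1.14 and 0.84 to 0.85 at 1.30, depending on how dispersion is set in the SME arm. The stated 0.80 is not reproduced, but it errs on the cautious side.

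**4. Ratio if index days are counted.** Ratio = (0.75m + r)/(m + r), where m is the control mean.

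| r (days) | m = 1.14 | m = 1.30 |
|---|---|---|
| 0 | 0.855/1.14 = 0.750 | 0.750 |
| 0.5 | 1.355/1.64 = 0.826 | 0.819 |
| 1.0 | 1.855/2.14 = 0.867 | 0.859 |
| 1.4 | 2.255/2.54 = 0.888 | 0.880 |
| 2.4 | 3.255/3.54 = 0.919 | 0.912 |

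At m = 1.14, a true 25% reduction would appear as 17% (r = 0.5), 13% (r = 1) or 8% (r = 2.4).

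**5. Absolute difference.** (1.14 + r) − (0.855 + r) = 0.285 days for every r.

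**6. Power if index days are counted.** Take exactly one added day per child. The SDs stay at 1.5 × 1.14 = 1.71 and 1.5 × 0.855 = 1.28, while the means rise to 2.14 and 1.855. The log ratio shrinks to 0.143, but its standard error shrinks to √[((1.71/2.14)² + (1.28/1.855)²)/100] = 0.106. The signal-to-noise ratio is 1.35, against 1.36 without index days. Only the spread in index days costs power. Simulated at m = 1.14 (1,500 runs each):

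| Added index days | Power |
|---|---|
| 0.5 on average (0 or 1) | 0.85 |
| 1, constant | 0.87 |
| 1 on average, Poisson | 0.82 |
| 1.4 on average (1 + Poisson 0.4) | 0.85 |
| 2.4 on average (1 + Poisson 1.4) | 0.78 |

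**7. Costs.** A shared index-stay cost would pull the cost ratio toward 1 in the same way. The documents give no cost figures, so this cannot be sized.

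**The case against.** The best reply is that the plan already excludes the index stay. Aim 1a is a definition of this same outcome, and it says so. The planning rates count readmissions and visits after discharge. Utilization comes mainly from monthly parental report of whether the child had been admitted, which for a child enrolled as an inpatient most naturally brings out new admissions; records serve to verify. The analysis text also considers zero-inflated models for children with no hospitalization or hospital cost during the study, which would describe almost nobody if index days counted.

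This stands as evidence of intent. A reader might infer from the Outcomes wording that index days will be counted and the result diluted. The documents do not support that: the Outcomes section is silent on the index stay and Aim 1a points the other way. Nor is there text showing that hospitalizations as a secondary outcome includes the index stay, or that the records and claims extract would include it.

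It is also fair that r is undocumented and could be near zero, that randomization balances index days in expectation so no false benefit arises, and that power hardly moves. What the reply does not remove is that the section defining the primary outcome omits the restriction that Aim 1a contains.

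**Conclusion.** The concern holds as an inconsistency in the primary outcome between Aim 1a and the planning rates on one side, and hypothesis 1 and the Outcomes section on the other. The consequence is conditional. If the Outcomes text is followed literally, the planned ratio of 0.75 would appear as 0.75 to 0.92 for an assumed 0 to 2.4 remaining index days; starting from a mean of 1.30 lowers the upper end only to 0.91. The result rests on that assumed range and on the inference that SME does not alter the index stay. The expected absolute difference is unaffected. Power for the 60% criterion is about 0.86 without index days and 0.78 to 0.87 with them.

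A reader might also infer that the year must start at discharge. It need not: the dilution comes from which days count, not from when the clock starts. The two start dates differ by at most 2.4/365 = 0.7% of the year under the same assumption.

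**What to change.** Before outcome data are seen:

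1. In hypothesis 1 and the Outcomes section, state that treatment days exclude the remainder of the index hospitalization and count only encounters after index discharge, as Aim 1a implies.
2. In the cost paragraph, state that index-stay costs are likewise excluded.
3. Use one start date throughout. Enrollment may stay as the start, provided the index stay is excluded. The power text should then say that rates counted from discharge stand in for the year from enrollment.
4. State that hospitalizations, as a secondary outcome, excludes the index stay, and how it differs from readmissions. Neither outcome needs to be dropped.

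The cost is a few sentences in a protocol amendment and a matching rule in the analysis code. The index discharge date should be available from the site's own records. No extra patients or contacts are needed.
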